To achieve 'unequivocal progression' on the basis of NTLs, there must be an overall level of substantial worsening in non-target disease such that, even in presence of SD or PR in TLs, the overall tumour burden has increased sufficiently to merit discontinuation of therapy. A modest 'increase' in the size of 1 or more NTLs is usually not sufficient to qualify for unequivocal progression status.

New Lesions

Details of any new lesions will also be recorded with the date of assessment. The presence of 1 or more new lesions is assessed as progression.

A lesion identified at a follow-up assessment in an anatomical location that was not scanned at baseline is considered a new lesion and will indicate disease progression.

The finding of a new lesion should be unequivocal: ie, not attributable to differences in scanning technique, change in imaging modality or findings thought to represent something other than tumour.

If a new lesion is equivocal, for example because of its small size, the treatment and tumour assessments should be continued until the new lesion has been confirmed. If repeat scans confirm there is a new lesion, then the progression date should be declared using the date of the initial scan.

Symptomatic Deterioration

Symptomatic deterioration is not a descriptor of an objective response: it is a reason for stopping study therapy.

Patients with 'symptomatic deterioration' requiring discontinuation of study treatment without objective evidence of disease progression at that time will undergo no further tumour

assessments in this study. Tumour response data for such patients will be censored at the date of their last RECIST assessment.

Evaluation of Overall Visit Response and Best Overall Response

The overall visit response will be derived using the algorithm shown in Table 4.

		NT T •	0 "
Target lesions	Non-Target lesions	New Lesions	Overall response
CR	CR	No	CR
CR	NA	No	CR
NA	CR	No	CR
CR	Non-CR/Non-progressive disease	No	PR
CR	NE	No	PR
PR	Non- progressive disease or NE	No	PR
SD	Non- progressive disease or NE	No	SD
NA	Non-CR/Non- progressive disease	No	SD (Non-CR/non- progressive disease)
NE	Non- progressive disease or NE	No	NE
NA	NE	No	NE
PD	Any	Yes or No	progressive disease
Any	progressive disease	Yes or No	progressive disease
Any	Any	Yes	progressive disease

Table 4Overall Visit Response

CR = complete response, PR = partial response, SD = stable disease, IR = incomplete response, NE = not evaluable, NA = not applicable (relevant when no TLs/NTLs at baseline)

Specifications for Radiological Imaging

These notes are recommendations for use in clinical studies. The use of standardised protocols for CT and MRI allows comparability both within and between different studies, irrespective of where the examination has been undertaken.

CT Scan

CT scans of the chest, abdomen, and pelvis should be contiguous throughout all the anatomical regions of interest.

The most critical CT image acquisition parameters for optimal tumour evaluation using RECIST 1.1 are anatomic coverage, contrast administration, slice thickness, and reconstruction interval.

Anatomic Coverage

Optimal anatomic coverage for most solid tumours is the chest, abdomen and pelvis. Coverage should encompass all areas of known predilection for metastases in the disease under evaluation and should additionally investigate areas that may be involved based on signs and symptoms of individual patients. Because a lesion later identified in a body part not scanned at baseline would be considered as a new lesion representing disease progression, careful consideration should be given to the extent of imaging coverage at baseline and at subsequent follow-up time points. This will enable better consistency not only of tumour measurements but also identification of new disease.

Intravenous Contrast Administration

Optimal visualisation and measurement of metastases in solid tumours requires consistent administration (dose and rate) of intravenous contrast as well as timing of scanning. Typically, most abdominal imaging is performed during the portal venous phase and (optimally) about the same time frame after injection on each examination. An adequate volume of a suitable contrast agent should be given so that the metastases are demonstrated to best effect and a consistent method is used on subsequent examinations for any given patient. It is very important that the same technique be used at baseline and on follow- up examinations for a given patient. For patients who develop contraindications to contrast after baseline contrast CT is done, the decision as to whether non-contrast CT or MRI (enhanced or non-enhanced) should be performed should also be based on the tumour type, anatomic location of the disease and should be optimised to allow for comparison to the prior studies if possible. Each case should be discussed with the radiologist to determine if substitution of these other approaches is possible and, if not, the patient should be considered not evaluable from that point forward. Care must be taken in measurement of TLs on a different modality and interpretation of non-target disease or new lesions, since the same lesion may appear to have a different size using a new modality. Oral contrast is recommended to help visualise and differentiate structures in the abdomen.

If iodine contrast media is medically contraindicated at baseline or at any time during the course of the study then the recommended methods are: CT thoracic examination without contrast and abdominal and pelvic MRI with contrast. If MRI cannot be performed then CT without intravenous contrast is an option for the thorax, abdomen and pelvic examinations.

Slice Thickness and Reconstruction Material

It is recommended that CT scans be performed at 5 mm contiguous slice thickness and this guideline presumes a minimum 5 mm thickness in recommendations for the measurable lesion

definition. Exceptionally, particular institutions may perform medically acceptable scans at slice thicknesses greater than 5 mm. If this occurs, the minimum size of measurable lesions at baseline should be twice the slice thickness of the baseline scans.

All window settings should be included in the assessment, particularly in the thorax where lung and soft tissue windows should be considered. When measuring lesions, the TLs should be measured on the same window setting for repeated examinations throughout the study. All images from each examination should be included in the assessment and not "selected" images of the apparent lesion.

MRI Scan

MRI has excellent contrast, spatial and temporal resolution; however, there are many image acquisition variables involved in MRI, which greatly impact image quality, lesion conspicuity and measurement. Furthermore, the availability of MRI is variable globally. The modality used at follow-up should be the same as was used at baseline and the lesions should be measured/assessed on the same pulse sequence. Generally, axial imaging of the abdomen and pelvis with T1 and T2 weighted imaging along with gadolinium-enhanced imaging should be performed. The field of view, matrix, number of excitations, phase encode steps, use of fat suppression and fast sequences should be optimised for the specific body part being imaged as well as the scanner utilised. It is beyond the scope of this Appendix to prescribe specific MRI pulse sequence parameters for all scanners, body parts and diseases. Ideally, the same type of scanner should be used and the image acquisition protocol should be followed as closely as possible to prior scans. Body scans should be performed with breath-hold scanning techniques if possible.

For these reasons, CT is the imaging modality of choice.

FDG-PET Scans

FDG-PET has gained acceptance as a valuable tool for detecting, staging and restaging several malignancies. If FDG-PET scans are included in a protocol, an FDG uptake period of 60 min prior to imaging has been decided as the most appropriate for imaging of patients with malignancy. Whole-body acquisition is important since this allows for sampling of all areas of interest and can assess if new lesions have appeared thus determining the possibility of interval progression of disease. Images from the base of the skull to the level of the mid-thigh should be obtained 60 min post injection. PET camera specifications are variable and manufacturer specific, so every attempt should be made to use the same scanner, or the same model scanner, for serial scans on the same patient. Whole-body acquisitions can be performed in either 2- or 3-dimensional mode with attenuation correction, but the method chosen should be consistent across all patients and serial scans in the clinical trial.

PET/CT Scans

At present, low dose or attenuation correction CT portions of a combined PET–CT are of limited use in anatomically based efficacy assessments and it is therefore suggested that they should not be substituted for dedicated diagnostic contrast enhanced CT scans for tumour measurements by RECIST 1.1. In exceptional situations, if a site can document that the CT performed as part of a PET–CT is of identical diagnostic quality to a diagnostic CT (with IV and oral contrast) then the CT portion of the PET–CT can be used for RECIST measurements. However, this is not recommended because the PET portion of the CT introduces additional data that may bias an Investigator if it is not routinely or serially performed.

REFERENCES

Eisenhauer et al, 2009

Wolchok et al, 2009

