5.1 Inclusion criteria

The inclusion criteria that are applicable to all parts/cohorts of the study are described in this section. Please refer to Section 13.1 for additional specific criteria applicable to Combination Module 1.

Informed Consent

- 1 Capable and willing to give signed informed consent which includes compliance with the requirements and restrictions listed in the ICF and in this protocol.
- 2 Provision of signed and dated written genetic informed consent prior to collection of sample for exploratory genetic analysis (optional).

The ICF process is described in Appendix A 3.

Age

3 Patient must be at least 18 years of age, at the time of signing the ICF.

Type of Patient and Disease Characteristics

- 4 Patients must have histological or cytological confirmation of advanced malignancy considered to be suitable for study treatment.
- 5 ECOG PS of 0 to 1.
- 6 Life expectancy greater than 12 weeks.
- 7 Progressive cancer at the time of study entry.
- 8 **PD expansion cohorts (or PD expansion subgroup)**: Patients must have at least one tumour suitable for biopsy and consent to having biopsies collected.

Reproduction

- 9 Negative pregnancy test (urine or serum) prior to start of dosing for women of child-bearing potential (WOCBP). Women of child-bearing potential are defined as women between menarche and menopause who have not been permanently or surgically sterilised and are capable of procreation.
- 10 Female patients must be post-menopausal, surgically sterile, or using an acceptable method of contraception (acceptable methods of contraception are defined in Section 5.3.3) for the duration of the study (from the time they sign consent) and for 12 weeks after the last dose of study treatment to prevent pregnancy.
- 11 For the duration of the study (from the time they sign consent) and for 12 weeks after the last dose of study treatment, sexually active male patients must be willing to use contraception as is defined in Section 5.3.3.

Post-menopausal is defined as:

• No menses for 12 months without an alternative medical cause. A high follicle stimulating hormone (FSH) level in the post-menopausal range may be used to confirm a

post-menopausal state in women not using hormonal contraception or hormonal replacement therapy. However in the absence of 12 months of amenorrhea, a single FSH measurement is insufficient.

- Radiation-induced oophorectomy with last menses greater than 12 months ago.

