5.3.3 Contraception

Male patients

- Should use barrier contraceptives (ie, by use of condoms) during sex with all partners from the time they sign consent and for 12 weeks after the last dose of study treatment. If male patients wish to father children, they should be advised to arrange for freezing of sperm samples prior to the start of study treatment.
- A sexual partner of a male participant who is a WOCBP should also use a highly effective form of contraception.
- Men should not donate sperm for 12 weeks after the last dose of study drug.

Female patients

- Women with evidence of non-child-bearing potential at screening have no restrictions around contraception.
- From the time of signing consent, and for 12 weeks after the last dose of study treatment; WOCBP and their partners (who are sexually active) should agree to use 2 reliable methods of contraception in combination, or they must totally/truly abstain from any form of sexual intercourse. All hormonal methods of contraception should be used in combination with the use of a condom by their male sexual partner for intercourse. Total/true abstinence is when a patient refrains from any form of sexual intercourse and this is in line with their usual and/or preferred lifestyle; this must continue for the total duration of the trial until at least 1 month after the last dose of study drug. Periodic abstinence (eg, calendar ovulation, symptothermal, post-ovulation methods, or declaration

of abstinence solely for the duration of the trial) and withdrawal are not acceptable methods of contraception.

- Contraceptives that are prone to drug-drug interactions may not be effective due to a potential CYP3A4 interaction with AZD7648. Contraception used must therefore include a condom and one of:
 - Medroxyprogesterone injections (eg, Depo-provera)
 - Intrauterine Device (IUD)
 - Levonorgestrol Intrauterine System (eg, Mirena)
 - Tubal occlusion
 - Vasectomised partner that is the sole sexual partner of the WOCBP trial participant provided the vasectomised partner has received medical assessment of the surgical success.

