13 STUDY POPULATION

13.1 Inclusion criteria

Patients are eligible to be included in the study only if all the inclusion criteria apply. **Please also refer to Section 5.1 for the inclusion criteria applicable to all modules in the study.** If the criteria in the modules is different from that in the Core Module criteria, the module-specific criteria should be followed. Inclusion criteria applicable to Combination Module 1 only are described in this section.

Part A and B

- 1 Patients must meet the eligibility criteria described in the Core Module.
- 2 Suitable for treatment with PLD as per local prescribing information.
- 3 Left ventricular ejection fraction above the institutional lower limit of normal, assessed by echocardiography or MUltiGated Angiography (MUGA).

Part B only

- 1 Provision of FFPE specimen from the primary tumour is mandatory. An archival tissue specimen is preferred but a new tissue sample may be used (if, for example, it is routine at a site to undertake biopsy of metastatic lesions). If an archival FFPE specimen is not available, a fresh tumour biopsy (FFPE) is mandatory.
- 2 Histologically confirmed advanced epithelial* ovarian, fallopian tube or primary peritoneal cancer which has relapsed within 12 months of completing a minimum of 4 cycles of platinum-containing chemotherapy regimen and for whom PLD is an appropriate therapy. Time to relapse after last platinum is based on Investigator assessment. Prior maintenance treatment is allowed and does not count as a line of therapy, including bevacizumab or PARPi, but treatment must be discontinued prior to study entry.
 - * Patients with carcinosarcoma histology may be included; patients with stromal, sex cord or germ cell tumours are excluded.
- 3 For platinum-resistant patients, ≤ 1 prior line of cytotoxic chemotherapy for the treatment of platinum-resistant disease. Patients must have had a radiological or CA-125 response to initial chemotherapy in the platinum-resistant setting, with no evidence of disease progression within 28 days of completing chemotherapy.

OR

For partially-platinum sensitive patients, there is no restriction on the number of prior lines of cytotoxic chemotherapy.

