13.3 Lifestyle restrictions

Restrictions for PLD should follow the institutional guidelines.

Please refer to Appendix G for contraception restrictions.

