Appendix G Acceptable Birth Control Methods

Pegylated liposomal doxorubicin is regarded as a compound with medium/high foetal risk.

Women of childbearing potential and their partners, who are sexually active, must agree to the use of one highly effective form of contraception [as listed below] and their partners must use a male condom. This should be started from the signing of the informed consent and continue throughout the period of taking study treatment and for 12 weeks after last dose of study drug(s), or they must totally/truly abstain from any form of sexual intercourse (see below).

Male patients must use a condom from the signing of the informed consent, during treatment and for 12 weeks after the last dose of study drug(s) when having sexual intercourse with a pregnant woman or with a woman of childbearing potential. Female partners of male patients should also use a highly effective form of contraception if they are of childbearing potential (as listed below). Male patients should not donate sperm throughout the period of taking study drug(s) and for 12 weeks following the last dose of study drug(s).

Acceptable non-hormonal birth control methods include:

- Total/True abstinence: When the patient refrains from any form of sexual intercourse and this is in line with their usual and/or preferred lifestyle; this must continue for the total duration of the trial and for 12 weeks after the last dose of study drug. Periodic abstinence (eg, calendar, ovulation, symptothermal, post-ovulation methods, or declaration of abstinence solely for the duration of a trial) and withdrawal are not acceptable methods of contraception.
- Vasectomised sexual partner PLUS male condom. Vasectomised partner is a highly effective birth control method provided that partner is the sole sexual partner of the WOCBP trial participant and that the vasectomised partner has received medical assessment of the surgical success.
- Tubal occlusion PLUS male condom.
- IUD PLUS male condom. Provided coils are copper-banded.

Acceptable hormonal methods:

- Normal and low dose combined oral pills PLUS male condom.
- Cerazette (desogestrel) PLUS male condom. Cerazette is currently the only highly efficacious progesterone based pill.
- Hormonal shot or injection (eg, Depo-Provera) PLUS male condom.
- Etonogestrel implants (eg, Implanon, Norplant) PLUS male condom.
- Norelgestromin / EE transdermal system PLUS male condom.

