- Intrauterine system [IUS] device (eg, levonorgestrel releasing IUS -Mirena®) PLUS male condom.

• Intravaginal device (eg, EE and etonogestrel) PLUS male condom.

Appendix H Guidelines for Evaluation of Objective Tumour Response Using RECIST 1.1 Criteria (Response Evaluation Criteria in Solid Tumours)

Introduction

This Appendix details the implementation of response evaluation criteria in solid tumours (RECIST) 1.1 guidelines (Eisenhauer et al, 2009) for the study with regards to Investigator assessment of tumour burden including protocol-specific requirements for this study.

Definition of Measurable, Non-measurable, Target and Non-target Lesions

Patients with at least 1 lesion (measurable and/or non-measurable) that can be accurately assessed at baseline by computed tomography (CT), MRI or plain X-ray should be included in this study. Patients with previously irradiated TLs can be included in this study provided that there has been progression in the irradiated site following the treatment.

Measurable Lesions

A lesion, not previously irradiated, that can be measured accurately at baseline as ≥ 10 mm in the longest diameter (except lymph nodes) which must have a short axis ≥ 15 mm with CT or MRI and which is suitable for accurate repeated measurements.

Non-measurable Lesions

- All other lesions, including small lesions (longest diameter < 10 mm or pathological lymph nodes with ≥ 10 mm to < 15 mm short axis at baseline). Nodes with < 10 mm short axis are considered non-pathological and should not be recorded as non-target lesions (NTLs).
- Truly non-measurable lesions include the following: bone lesions, leptomeningeal disease, ascites, pleural/pericardial effusion, inflammatory breast disease, lymphangitic involvement of skin or lung, abdominal masses/abdominal organomegaly identified by physical examination that are not measurable by CT or MRI.
- Previously irradiated lesions as localised post-radiation changes, which affect lesion sizes, may occur. Therefore, lesions that have been previously irradiated will not be considered measurable and should be selected as NTLs at baseline and followed up as part of the NTL assessment.
- Skin lesions assessed by clinical examination.
- Brain metastasis.

Special Cases

• Lytic bone lesions or mixed lytic-blastic lesions, with identifiable soft tissue components, can be considered measurable if the soft tissue component meets the definition of measurability. Blastic lesions are considered non-measurable.

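### Appendix G offers women on AZD7648 plus PLD five hormonal contraceptives that are not on the closed, CYP3A4-driven list in Section 5.3.3, to which inclusion criterion 10 binds them

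*Protocol*

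**What the plan says.** Section 5.3.3 gives a pharmacological reason for its list: "Contraceptives that are prone to drug-drug interactions may not be effective due to a potential CYP3A4 interaction with AZD7648". It then closes the list: "Contraception used must therefore include a condom and one of" five methods, namely medroxyprogesterone injection, an IUD, the levonorgestrel intrauterine system, tubal occlusion, or a vasectomised sole partner. True abstinence is the alternative.

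Inclusion criterion 10 (Section 5.1) makes this an eligibility rule, since "acceptable methods of contraception are defined in Section 5.3.3". Section 5.1 says its criteria apply to all parts and cohorts. For Combination Module 1, Section 13.1 repeats the obligation: "Patients must meet the eligibility criteria described in the Core Module". It adds no contraception criterion of its own.

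Section 13.3 then points the same module elsewhere: "Please refer to Appendix G for contraception restrictions". Appendix G lists seven hormonal methods as acceptable, each with a male condom. They include "Normal and low dose combined oral pills PLUS male condom" and "Intravaginal device (eg, EE and etonogestrel) PLUS male condom".

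**The concern.** One protocol gives two different lists to the same women. The narrower list exists because AZD7648 might undermine some contraceptives, and Module 1 patients take AZD7648. The wider list is the one the module's own lifestyle section names, so it is the one a Module 1 site is likely to use.

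Two things are at stake. The first is safety: a woman could rely on a method the protocol itself regards as possibly weakened by AZD7648 while also receiving PLD, which Appendix G describes as carrying medium to high foetal risk. The second is eligibility: she would not meet criterion 10. Section 5 allows no exceptions to the entry criteria, and SAP Section 2.3 names deviation from key entry criteria as a possible important protocol deviation.

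**Working it through.** No calculation in the plan bears on this, so the check is an item-by-item comparison of the two lists.

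| Hormonal method in Appendix G (each with condom) | On the Section 5.3.3 list? |
|---|---|
| Combined oral pill | No |
| Desogestrel pill | No |
| Injection (example given: Depo-Provera) | Yes |
| Etonogestrel implant | No |
| Norelgestromin/EE patch | No |
| Levonorgestrel intrauterine system | Yes |
| Intravaginal device (EE and etonogestrel) | No |

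There are 7 hormonal methods in Appendix G, of which 2 are on the Section 5.3.3 list, so 7 − 2 = 5 are not. Appendix G words the injection more broadly than Section 5.3.3 does, but its example is a listed product, so it is counted as a match.

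**Which list binds a Module 1 patient?** Criterion 10 applies to all cohorts and refers to Section 5.3.3, and Section 13.1 requires the Core criteria to be met. The binding list is therefore the one in Section 5.3.3. Section 5.3.3 does contain a general sentence that hormonal methods should be combined with a condom. The bullet that follows narrows the choice to the five named methods, so the general sentence does not reopen it.

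**Has the interaction question been settled in a way that would clear the five methods?** No. CYP3A4 induction by AZD7648 is a secondary objective (Protocol Section 3). The marker, 4β-hydroxy cholesterol, is sampled only in monotherapy (Section 8.5.2), and the SAP will only list it, for the Core Module (SAP Sections 3.2.1.9 and 4.2.1).

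**A separate slip on duration.** Criterion 10, the opening of the relevant bullet in Section 5.3.3, and Appendix G all give 12 weeks after the last dose. The abstinence clause inside that same Section 5.3.3 bullet says "until at least 1 month after the last dose of study drug". Twelve weeks is 12 × 7 = 84 days; a month by the SAP's convention (Section 3.1) is 30.4375 days. The clause sets a floor and does not contradict a 12-week duty, but a Core Module reader could take it as sufficient.

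**The case against.** The strongest reply is that the module sections only add to Sections 1 to 9. On a cumulative reading a Module 1 woman must satisfy both texts, the narrower list governs, and Appendix G permits nothing extra. That is a sound reading of what binds, but Appendix G still tells the site that the five methods are acceptable, and Section 13.3 does not say it must be read together with Section 5.3.3.

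The opposite reply is that module-specific criteria take precedence where they differ, and that the version 4.0 change log says Appendix G was updated for this module, so the wider list may be deliberate. That rule concerns eligibility criteria, and Section 13.1 contains none on contraception. If Appendix G did prevail, the protocol would be allowing methods it describes as possibly ineffective with AZD7648, with no reason given.

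Several points about size do stand:

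- The interaction is only potential, and the documents do not say how far each of the five methods would be affected.
- The starting Module 1 schedule gives at most 25% of the continuous monotherapy dose per cycle (Section 12.3.1). Section 5.3.3 makes no exception for lower exposure, however, and after six PLD cycles patients may continue AZD7648 at up to the monotherapy RP2D (Section 12.1).
- A condom accompanies every method except abstinence. Because both lists require it, it does not replace the restriction on the second method.
- Pregnancy tests are scheduled before and during treatment (Table 13). They detect pregnancy and do not prevent it.
- SAP Section 1.1 reports that development has been halted, and SAP Section 1.2 now covers only Part A of the module, which limits how many future patients an amendment would reach.

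**Conclusion.** The concern holds. Five of the seven hormonal methods in Appendix G are off the list that criterion 10 makes binding, and on either reading of precedence the text is defective. It is an internal inconsistency with a patient-safety and eligibility consequence, minor to moderate in size, and it touches no endpoint, sample size or analysis. The one-month clause is a secondary wording error.

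The conclusion rests on taking Section 5.3.3's own rationale at face value; it makes no independent claim about the pharmacology of any method. How urgent the change is depends on whether any woman is still being dosed or is within 12 weeks of her last dose, which the documents do not state.

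**What to change.** In Appendix G, for women taking AZD7648, delete combined oral pills, desogestrel, etonogestrel implants, the norelgestromin/EE patch and the intravaginal device, so that the hormonal options match Section 5.3.3. Appendix G's list also serves female partners of male patients, who do not take AZD7648; if the five methods are to stay for them, place them under a separate partner-only heading. In Section 5.3.3, change the abstinence period after the last dose from one month to 12 weeks.

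This is amendment wording and needs no new procedures. The cost falls on Module 1 women, who would have fewer permitted methods; anyone already relying on one of the five would have to switch to a listed one.
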